## **ESP vs. PVB Nerve Blocks for Video Assisted Thoracoscopic Surgery (VATS) Research Protocol**

Continuous paravertebral analgesia and erector spinae plane blockade (ESP) are accepted techniques at UPMC for pain management in thoracic surgery. This is a prospective randomized study intended to assess the efficacy, safety and side-effect profile of continuous ESP block Vs continuous paravertebral block for VATS procedures.

### **Methods:**

Once the patient has agreed to have peripheral nerve blocks as part of the analgesia technique and meets inclusion criteria, the patient will be asked to participate in the study. If they agree to participate, informed consent will be obtained and we will proceed with randomization.

### **Patient selection and Inclusion/Exclusion criteria**

#### ***Inclusion criteria:***

- \* Patients undergoing VATS agreeable to have a nerve block as analgesic technique
- \* Age: 18 years old and older.
- \* ASA I-IV

#### ***Exclusion criteria:***

- \* Cognitive impairment that would not allow effective nerve block placement or gathering information related to the study (ex. pain score).
- \* Contraindications for nerve block placement such as coagulopathy, use of clopidogrel in the past 48hs, patients on dual antiplatelet therapy, infection at the site of puncture, patient refusal, allergy to local anesthetics.
- \* Chronic opiate consumption (>30 OME/day)
- \* Patient expected to be on therapeutic anticoagulation post procedure.
- \* Pregnancy
- \* Comorbid conditions: Any comorbid condition that in the judgment of the anesthesiologist would preclude the patient from any aspect of the study (ex. sepsis, possibly abnormalities of the thoracic spine or paravertebral anatomy such as neoplastic mass occupying the space, empyema, increased intracranial pressure)

**Randomization:** Patients will be randomized 1:1 into one of the study groups. The groups will be defined as Group 1: ESP block; Group 2: PVNB.

The goal is to include 80 patients (40 in each arm).

Before insertion of catheter, ropivacaine 0.5% will be injected incrementally prior aspiration to decrease the risk of intravascular injection every 5ml. The dose will be left at discretion of the

anesthesiologist performing the nerve block, with a volume that would provide effective dermatome coverage and considering the maximum possible dose to avoid local anesthetic toxicity. After administration of LA catheter will then be placed and left 5cm beyond the needle tip.

**Continuous Infusion:** bupivacaine 0.0625% will be started at 6ml/h and will be titrated up to a max of 12ml/h.

**Bolus:** patients will have access to rescue boluses of 3ml every hour, through the catheter with bupivacaine 0.0625% if needed.

All patients will be assessed daily by the acute pain service. Additional pain medication will be available to all patients per standard of care. All patients will have access to acetaminophen 1g every 6hs, ketamine infusion, and opiates as needed to provide adequate analgesia.

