## **Data collection**

### ***Preoperative period:***

In addition, to treat breakthrough pain, all patients will receive multimodal analgesia per routine.

An excel sheet will be available to collect the patient information from EMR and the patient.

- Data to be collected: age, gender, type of surgery, type of anesthesia (including medications and type regional anesthesia received).
- Incentive spirometer baseline measure prior to surgery
- dermatomal spread (pinprick and or changes in temperature (cold or hot) sensation) after 15-20mins of initial bolus will be documented.

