### **Postoperative period**

- total opioid consumption (in morphine equivalents) and pain scores on the numeric pain rating scale will be documented every 6hs for the first 24hs.
- Incentive spirometer daily score postoperatively
- Length of stay,

- Duration of catheter
- Use of additional pain medication will be recorded
- Document adverse events or complications related to nerve blocks
- dermatome spread with infusion infusion will be documented.

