**STATISTICAL ANALYSIS PLAN – 01/03/2020**

## **Statistical Analysis Plan**

The number of 80 total patients (40 in each arm) is similar to many studies that have been adequately powered to detect a clinical difference between nerve blocks. For example, Jaegar et al 2013 Volume 38 Issue 6 discovered a significant difference between muscle strength in femoral nerve versus adductor canal block with a total of 54 patients. 80 patients were chosen because we are hoping to achieve a power of 80%. Previous studies have identified mean opioid consumption in patients undergoing VATS procedure and receiving normal paravertebral nerve blocks is approximately 100mg OME. We hope in our experimental group to detect a difference in mean opioid consumption (10% or more ideally). Based on our goal power of the study, we would need a sample size of 32 patients. After surveying the volume of patients undergoing this procedure at our intended site, we deemed that it would be possible to recruit 60 patients for this study in a reasonable period of time. For parametric data we will use a t-test. For non-parametric data we will use a Mann-Whitney U Test. For categorical data we will use a chi-square test. We may use a log regression evaluation if needed. We will use repeated measures ANOVA test to compare repeated measures for each patient. Statistical data will be analyzed using SAS software.

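### Home opioid dose (up to 30 OME/day is eligible) is not recorded, and no baseline covariate enters the planned opioid comparison: an avoidable loss of precision, not a bias

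*Protocol*

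**What the plan says.** - **Eligibility.** The protocol's exclusion criteria remove "Chronic opiate consumption (>30 OME/day"). Any home use from 0 to 30 OME/day remains eligible.
- **Baseline data.** The preoperative list reads "Data to be collected: age, gender, type of surgery, type of anesthesia (including medications and type regional anesthesia received"). It adds "Incentive spirometer baseline measure prior to surgery" and dermatomal spread after the initial bolus. Home opioid dose is not listed. The mention of medications sits inside the parenthesis on anesthesia, so its natural reading is anesthetic drugs.
- **Opioid outcome.** Intraoperative and PACU opioid use is recorded. After that, "total opioid consumption (in morphine equivalents) and pain scores on the numeric pain rating scale will be documented every 6hs for the first 24hs".
- **Target.** The SAP puts mean consumption in patients "receiving normal paravertebral nerve blocks is approximately 100mg OME" and hopes to "detect a difference in mean opioid consumption (10% or more ideally"), which is about 10 mg.
- **Analysis.** "For parametric data we will use a t-test", with Mann-Whitney for non-parametric data. Chi-square and repeated measures ANOVA are also listed. The only regression is an optional one with no outcome, covariate or trigger named.
- **Allocation.** The protocol randomizes 1:1, with no stratification stated.

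**The concern.** The exclusion criterion shows that the investigators regard chronic opioid use as relevant, and applying it means judging each patient's home dose against a number. Below the cut-off, the plan then drops the measure. It is expressed in OME, as the SAP's opioid figures are, so it is an obvious candidate covariate. Age and type of surgery are gathered but given no role in the opioid comparison.

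What is at stake is the width of the confidence interval for a hoped-for difference of about 10 mg. A covariate that predicts the outcome reduces residual variance if it is in the model. If it is left out, that variance stays in the standard error. If home dose is never recorded, the trial also cannot describe how the arms compare on it, and later adjustment would mean going back to the charts.

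**Working it through.** **Inputs from the documents.** Planned size is 40 per arm (protocol and SAP). The target is 10% of about 100 mg, or 10 mg (SAP). Power is 80% and the stated requirement is 32 patients (SAP).

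**Inputs assumed.** Two-sided alpha of 5%, outcome SD, SD of home dose, and the share of variance explained by covariates (R²). None of these is stated.

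**Step 1: the SAP's own figure.** The 32 cannot be reproduced without an SD and alpha. It can be inverted for the SD it implies, using SD = 10 × √(n/2) / (1.96 + 0.84), with n per arm:
- 32 per arm: 10 × 4.00 / 2.80 = 14.3 mg.
- 32 in total (16 per arm): 10 × 2.83 / 2.80 = 10.1 mg.

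The working range should therefore include these values as well as larger ones such as 20 and 30 mg.

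**Step 2: power with and without covariates.** Residual SD = SD × √(1 − R²). Power is from the noncentral t with 40 per arm, a 10 mg difference and two-sided 5%. The few degrees of freedom used by the covariates are ignored.

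| Outcome SD | R² = 0 | R² = 0.01 | R² = 0.3 (residual SD) |
|---|---|---|---|
| 14.3 mg | 87% | 87% | 96% (11.96) |
| 20 mg | 60% | 60% | 75% (16.73) |
| 30 mg | 31% | 32% | 42% (25.10) |

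At SD 10.1 mg, unadjusted power is already 99%. The SAP also says 60 patients could be recruited. At 30 per arm and SD 20, power goes from 48% to 62% at R² = 0.3.

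**Step 3: how much could home dose supply alone?** Assume a home-dose SD of 5 to 10 mg, with each home mg adding a full 1 mg to the outcome. Then R² = (home SD / outcome SD)²:
- Outcome SD 20: R² = 25/400 to 100/400 = 6% to 25%. Power rises from 59.8% to 62.6-72.2%.
- Outcome SD 30: R² = 25/900 to 100/900 = 3% to 11%. Power rises from 31.3% to 32.1-34.5%.

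A home SD of 10 mg is generous. If a share p of patients are users, spread evenly over 0 to 30, the variance is 300p − 225p². This peaks at 100 (SD 10) when p = 2/3. At p = 0.2 it is 60 − 9 = 51, an SD of 7.1. An R² of 0.3 therefore needs age and type of surgery to contribute too, above all at the larger outcome SDs.

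**Step 4: chance imbalance.** The SE of the difference in mean home dose is SD × √(2/40), which is 1.12 for SD 5 and 2.24 for SD 10. The 95% ranges are ±2.2 and ±4.4 mg. This is not additional to the outcome's standard error. At outcome SD 20 that SE is 20 × √(2/40) = 4.47. Removing a 2.24 mg home-dose component leaves √(20 − 5) = 3.87, which equals the adjusted SE, 17.32 × √(2/40). The imbalance is part of the 4.47, so it has already been counted.

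**The case against.** The strongest reply is that an unadjusted comparison in a randomized trial is correct. It is unbiased and the t-test holds its type I error, so nothing here is an error. The exclusion already removes the heaviest users and bounds the rest at 30 OME/day. If home dose correlates with the outcome at only r = 0.1 (R² = 0.01), adjustment gains less than one point of power. If the SD is as small as the SAP's 32 patients implies, the trial has 87% to 99% power at 40 per arm without adjustment. All of this stands, and it limits the point to efficiency.

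Three stronger readings are tempting and should not be drawn:

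- **That imbalance in home use could pass for a block effect and so bias the trial.** A single result can be shifted by chance, but the standard error already allows for it (step 4).
- **That 30 OME/day is three times the target and therefore swamps it.** This sets one patient's dose against a difference in arm means. One such patient among 40 moves an arm mean by 30/40 = 0.75 mg.
- **That home dose is an established strong predictor.** The documents say nothing about its relation to postoperative use, so the full pass-through in step 3 is an assumption.

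It may also be said that home medication could be retrieved later, since the protocol draws data from the medical record and the patient. That is possible but not planned. Equally, the eligibility rule requires only a judgement above or below 30, so an exact dose may not be to hand unless it is asked for.

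The objection does not remove the gap. The covariate is not on the collection list, the optional regression names no covariate, and age and type of surgery go unused although they are already collected.

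**Conclusion.** The point holds as a low-cost improvement in precision. The planned test is valid, and what is lost is efficiency. At 40 per arm, a 10 mg difference and two-sided 5%, a total covariate R² of 0.01 to 0.3 gives power of 60-75% instead of 60% (SD 20), 32-42% instead of 31% (SD 30), or 87-96% instead of 87% (SD 14.3). In terms of the confidence interval, √(1 − R²) makes it about 0.5% narrower at R² = 0.01 and about 16% narrower at R² = 0.3.

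Alpha, outcome SD and R² are all assumptions, and the documents cannot narrow these ranges. A reader might infer that adjustment would secure the 80% power goal. It would not at an SD of 20 mg or more under these assumptions. The missing SD is the larger gap in the plan.

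**What to change.** 1. Add preoperative daily OME to the existing Excel sheet, entered when the 30 OME/day exclusion is checked, with zero recorded explicitly for non-users.
2. In the SAP, before analysis, name ANCOVA as the comparison of postoperative opioid consumption (log scale if skewed). The terms are treatment, preoperative OME, age and type of surgery, the last in a few levels defined in advance.
3. Keep the unadjusted t-test or Mann-Whitney test as a sensitivity analysis.

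The cost is one data field, a short SAP statement and a few degrees of freedom out of 60 to 80 patients, slightly more if type of surgery has several levels. No clinical management changes. If few enrolled patients use opioids at home, and age and type of surgery predict little, the gain will be negligible.

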### ***Postoperative period:***

In PACU:

- Intraoperative opiate consumption in (morphine equivalent dose) and while in PACU.
- pain scores using the numeric rating scale.
- insertion site and number of catheters will be documented
- dermatomal spread (pinprick and or changes in temperature (cold or hot) sensation) will be documented.
- number of chest tubes and sites

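### Any VATS procedure is eligible, but opioid consumption is compared with unadjusted tests, so variation due to surgical extent stays in the error term and costs precision

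*Protocol*

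**What the plan says.** Eligibility is broad. The first inclusion criterion is "Patients undergoing VATS agreeable to have a nerve block as analgesic technique", with no limit on the kind or extent of operation. The Randomization paragraph, printed under the exclusion criteria, says "Patients will be randomized 1:1 into one of the study groups" and names no stratum, block or minimisation factor. The target is stated as "The goal is to include 80 patients (40 in each arm").

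The procedure is recorded. The preoperative data list includes "age, gender, type of surgery, type of anesthesia", drawn from the medical record and the patient. It does not say whether the operation entered is the planned one or the one carried out. The PACU list adds "number of chest tubes and sites", but neither the PACU list nor the later postoperative list has an explicit item for the procedure performed or for conversion to an open incision.

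The SAP sizes the trial on opioid consumption. It puts the mean in patients "receiving normal paravertebral nerve blocks is approximately 100mg OME" and states the aim as "We hope in our experimental group to detect a difference in mean opioid consumption (10% or more ideally"). The named comparisons are a t-test for parametric data and a Mann-Whitney test otherwise. A regression is mentioned only as a possibility, without covariates. No SD, significance level, procedure mix or opioid use by procedure is given.

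**The concern.** Collecting type of surgery implies that the sponsor expects more than one kind of operation. If larger operations need more opioid than smaller ones, part of the patient-to-patient spread in consumption is predictable from something known before randomization. An unadjusted test leaves that part in the standard error. The target is small, about 10 mg (10% of about 100 mg), so avoidable noise matters. A result with visibly unequal surgical mix between arms would also be harder to interpret if no adjustment had been specified in advance.

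**Working it through.** **Inputs from the documents.** Mean about 100 mg OME and target 10%, hence a difference of 10 mg; 40 per arm; aimed power 80%.

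**Assumptions, because the documents are silent.** Two-sided 5% level; share of larger operations p = 30% to 50%; extra opioid after a larger operation D = 20 to 40 mg; within-type SD s = 13, 20 or 30 mg.

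**1. The SAP's own figure.** The stated need for 32 patients cannot be reproduced without an SD. From n per arm = 2(1.96 + 0.842)² SD² / 10², the implied SD is 10.1 mg if 32 is the total (16 per arm) and 14.3 mg if it is per arm.

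**2. Power without and with adjustment.** Unadjusted, the total SD is √(s² + p(1−p)D²). With the procedure in the model, the SD is s, on 77 degrees of freedom. The standard error is SD × √(2/40) under balance, and power comes from the noncentral t distribution. For s = 20:

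- p = 0.3, D = 20: total SD √(400 + 84) = 22.0, SE 4.92 mg, power 52%.
- p = 0.5, D = 40: total SD √(400 + 400) = 28.3, SE 6.32 mg, power 35%.
- Adjusted and stratified: SD 20, SE 4.47 mg, power 59.8%.
- Adjusted, not stratified (averaged over the exact chance split of larger operations between arms): 59.3%.

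| Within-type SD | Unadjusted | Adjusted, unstratified | Adjusted, stratified |
|---|---|---|---|
| 13 mg | 46% to 79% | 92.1% | 92.5% |
| 20 mg | 35% to 52% | 59.3% | 59.8% |
| 30 mg | 23% to 29% | 31.0% | 31.3% |

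Nearly all the gain comes from the covariate. Stratified allocation adds about half a point or less.

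**3. The same question with the total SD held fixed.** At a total SD of 16 mg, where 40 per arm gives 80% power, a procedure factor explaining 10%, 20% or 30% of the variance raises power to 84%, 88% or 92%. At 14.3 mg, power rises from 88% to 91%, 94% or 96%. At 30 mg it rises from 32% to 35%, 38% or 43%.

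**4. Size of a chance imbalance.** With 24 or 40 larger operations among 80 patients, the SD of the between-arm difference in their share is 0.103 or 0.113. Multiplied by D, the 95% range of the shift in the mean difference is ±4.0 to ±8.8 mg. The exact (hypergeometric) chance of a shift of 8 mg or more is under 0.1% at D = 20 and 9% to 12% at D = 40. For 10 mg or more it is about 0% and 3% to 4%. At the SDs implied by the SAP's 32, the 95% limit is 1.96 × SD × √(2/40) = 4.4 or 6.3 mg, even if the procedure explained all the variance.

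**5. Validity.** In simulation with no treatment effect, the unadjusted t-test rejected in 5.0% of trials at D = 20 and 4.7% at D = 45.

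**The case against.** The best defence is that nothing here is an error. Broad eligibility and simple 1:1 randomization are defensible choices, the t-test keeps its error rate, and its standard error already allows for chance imbalance. That stands. It is also fair that the low-power corners need strong assumptions. Power of 35% at a within-type SD of 20 mg requires a two-level procedure factor to explain half the opioid variance, and 46% at 13 mg requires 70%. The missing SD and significance level, and the conflict between 32, 60 and 80 patients in the SAP, matter more than this point.

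A reader might infer three stronger things, and the documents support none of them:

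- **That imbalance in surgical extent can approach the 10 mg target.** This needs an assumed procedure effect of about 40 mg or more and an imbalance at the edge of its range.
- **That missing stratification is the main defect.** Silence in a short protocol shows that stratification is unspecified, not that it is ruled out, and it would add almost nothing once the covariate is in the model.
- **That only the planned operation is recorded.** The bullet that lists type of surgery also covers regional anesthesia received, which is not a preoperative plan. Planned or performed is simply not specified. Chest tubes are a partial marker of extent, although they identify neither the procedure nor a conversion.

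What remains is that a baseline factor likely to predict the outcome is collected and then left unused in the named tests, although using it is nearly free.

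**Conclusion.** The point holds as a loss of precision, not as a bias or an invalid test. Under the stated assumptions, with a within-type SD of 20 mg, adjustment takes power for 10 mg from about 35% to 52% up to about 59% to 60%. The gain depends on figures the documents do not give. It can be larger at 13 mg, and at 30 mg it is only about 2 to 8 points. Adjustment does not rescue a trial that is too small for its true SD. It is a worthwhile improvement at very low cost, secondary to settling the SD, the significance level and the sample size.

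**What to change.** In the SAP, make the main opioid comparison a linear model (ANCOVA) with treatment and planned procedure type as factors, in all randomized patients. Classify planned type before randomization into categories fixed in advance, for example anatomical resection versus other VATS. That split is only an illustration, since the documents define none.

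In the protocol's preoperative data list, state that the type used as covariate is the planned one. Add the procedure performed and any conversion to open, taken from the operative record. Because these are settled after allocation, use them for description and one supporting analysis only, not as covariates in the main model.

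Stratifying the 1:1 allocation by the same factor is optional. If it is used, or is already in use, say so and keep the stratum in the model.

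The cost is one model term, two chart fields and the need to classify the planned procedure before randomization, plus a two-stratum list if stratification is chosen. No patients are added.

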## **Data collection**

### ***Preoperative period:***

In addition, to treat breakthrough pain, all patients will receive multimodal analgesia per routine.

An excel sheet will be available to collect the patient information from EMR and the patient.

- Data to be collected: age, gender, type of surgery, type of anesthesia (including medications and type regional anesthesia received).
- Incentive spirometer baseline measure prior to surgery
- dermatomal spread (pinprick and or changes in temperature (cold or hot) sensation) after 15-20mins of initial bolus will be documented.

### ***Postoperative period:***

In PACU:

- Intraoperative opiate consumption in (morphine equivalent dose) and while in PACU.
- pain scores using the numeric rating scale.
- insertion site and number of catheters will be documented
- dermatomal spread (pinprick and or changes in temperature (cold or hot) sensation) will be documented.
- number of chest tubes and sites

### **Postoperative period**

- total opioid consumption (in morphine equivalents) and pain scores on the numeric pain rating scale will be documented every 6hs for the first 24hs.
- Incentive spirometer daily score postoperatively
- Length of stay,

- Duration of catheter
- Use of additional pain medication will be recorded
- Document adverse events or complications related to nerve blocks
- dermatome spread with infusion infusion will be documented.

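### Safety and side effects are part of the objective, but the one adverse-event item appears limited to block-related events, so the comparison between arms can be distorted by attribution

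*Protocol*

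**What the plan says.** The Protocol's opening paragraph describes a randomized study "intended to assess the efficacy, safety and side-effect profile of continuous ESP block Vs continuous paravertebral block for VATS procedures". Safety and side effects thus stand beside efficacy.

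The Data collection section has three lists:

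- **Preoperative period.** The only item tied to block placement is "dermatomal spread (pinprick and or changes in temperature (cold or hot) sensation) after 15-20mins of initial bolus will be documented". There is no adverse-event item.
- **Postoperative period, PACU.** This covers opioid use (including intraoperative use), pain scores, catheter details ("insertion site and number of catheters will be documented"), dermatomal spread and chest tubes. There is no adverse-event item.
- **Postoperative period, final list.** This holds the only safety item: "Document adverse events or complications related to nerve blocks". It gives no definitions, time window, assessor or rule for deciding relatedness.

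The treatment paragraphs after the Exclusion criteria recognise a hazard at placement: "ropivacaine 0.5% will be injected incrementally prior aspiration to decrease the risk of intravascular injection every 5ml". They also set up a regular contact: "All patients will be assessed daily by the acute pain service".

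On allocation, the Protocol says "Patients will be randomized 1:1 into one of the study groups". Neither document mentions masking of patient, operator or assessor. The SAP assigns a chi-square test to categorical data in general and names no safety endpoint or safety comparison.

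**The concern.** When relatedness is the condition for recording an event, rather than something noted about an event already recorded, the data hold only what the attributor let through. After thoracic surgery, hypotension, nausea or a respiratory event can plausibly be put down to the operation, the anesthetic, opioids or the block. If the person deciding knows which block was given, the threshold for blaming it may differ between arms. A difference could then appear, shrink or grow without any difference in what happened to patients. Events that were never written down may not be recoverable at analysis.

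There are two lesser gaps. A side-effect profile would ordinarily include common effects such as nausea or sedation, and no list asks for them. And at the stages where placement complications would first be seen, no item prompts anyone to record them.

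**Working it through.** The documents state no adverse-event rate, safety power or safety sample size, so there is no figure of theirs to reproduce. The check has two parts.

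**1. Objective against data lists**

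| Stage | Adverse-event item? | General side-effect item? |
|---|---|---|
| Placement and 15-20 min after the bolus (Preoperative period) | No | No |
| Intraoperative and PACU (Postoperative period, PACU) | No | No |
| Later postoperative period (final list) | Yes, apparently limited to block-related events | No |
| SAP | Generic chi-square test only | No |

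The single item has no time window. A puncture or injection complication is by nature block-related, so it falls within the wording and could be entered later. What is lacking is a prompt at the time.

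**2. What a relatedness filter can do (illustration only)**

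Inputs: 40 patients per arm (Protocol). Everything else is assumed: the true rates, the attribution probabilities and a two-sided alpha of 0.05, since the documents give none of these.

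Recorded rate = true rate × probability that an event is attributed to the block.

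*Equal true rates, 80% v 50% attribution:*

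| True rate, both arms | Recorded, 80% attributed | Recorded, 50% attributed | Spurious difference |
|---|---|---|---|
| 10% | 0.10 × 0.80 = 8% | 0.10 × 0.50 = 5% | 3 points |
| 20% | 0.20 × 0.80 = 16% | 0.20 × 0.50 = 10% | 6 points |
| 30% | 0.30 × 0.80 = 24% | 0.30 × 0.50 = 15% | 9 points |

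The spurious difference is the true rate times the gap in attribution. At a true rate of 20%, each 10-point gap adds 0.20 × 0.10 = 2 points, and equal attribution adds none.

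*Is the spurious difference likely to be significant?* For 16% v 10%, the pooled rate is 13%, the standard error is √(0.13 × 0.87 × 2/40) = 0.075, and z = 0.06/0.075 = 0.8 (p about 0.4). For 24% v 15%, the pooled rate is 19.5%, the standard error is 0.089, and z is about 1.0 (p about 0.3). Usually it would not be.

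*A real difference, 30% v 10%.* Power = Φ[(difference − 1.96 × SE₀)/SE₁], with SE₀ from the pooled rate and SE₁ from the separate rates.

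- All events recorded (30% v 10%): SE₀ = 0.0894, SE₁ = 0.0866, power = Φ(0.285) = 61%.
- Half recorded in each arm (15% v 5%): SE₀ = 0.0671, SE₁ = 0.0661, power = Φ(−0.476) = 32%.
- 80% recorded in the higher-rate arm and 50% in the other (24% v 5%): power 68%, with the difference in proportional terms exaggerated (4.8-fold instead of 3-fold).
- 50% recorded in the higher-rate arm and 80% in the other (15% v 8%): power 16%, with the difference largely hidden.

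So the filter can weaken, exaggerate or mask a real difference, and even-handed filtering still loses information.

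**The case against.** **Insertion events.** A reader might infer that events at block insertion are lost by design because the item sits in the last list. The documents do not support that. The item has no time window, the PACU list itself gathers earlier facts such as intraoperative opioid use, and data are also drawn from the medical record. What stands is that capture is not prompted.

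**Grammar.** The qualifier about relatedness could attach only to complications, leaving all adverse events in scope. That reading is possible but less natural. If it is the intended one, the text should say so, since two data collectors could apply opposite rules.

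**Masking.** A reader might conclude that the attributor is unmasked and expects one block to be riskier. The documents say neither. They name no attributor and express no such expectation. The operator must know which block was placed, but for anyone else lack of masking is an inference from silence.

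**Scope.** The objective can be read as the side effects of the blocks themselves, which a block-related item would match. This is fair, and it rules out saying that the objective cannot be answered. It does not remove the dependence on attribution, because someone must still decide which events belong to the block.

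**Numbers.** The 80% v 50% split is invented, and the resulting spurious differences would usually not reach significance with 40 per arm. This stands: the figures show a mechanism, not an expected bias. The limited precision of 40 per arm would apply under perfect recording too, and is no evidence for this point.

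**Conclusion.** The point holds as a gap between the objective and the data collected. The single safety item, read naturally, makes recording depend on a relatedness judgement for which the plan gives no rule, no assessor and no masking. General side effects have no item, and capture of placement-stage complications is not assured. The SAP names no safety comparison that would make up for this.

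The size cannot be estimated from the documents. Under the assumed attribution probabilities, equal true rates of 10% to 30% would be recorded with spurious differences of 3 to 9 points, and power for a real 30% v 10% difference would range from 16% to 68%, against 61% with full recording. The conclusion rests on the natural reading of the item and on the absence of any statement about masking. It does not rest on those rates. This is a cheap improvement worth making, not a flaw that invalidates the trial.

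**What to change.** 1. **Protocol, Data collection.** Replace the adverse-event item with a short prespecified list of adverse events and side effects, completed for every patient in both arms regardless of presumed cause. The investigators should settle the items.
2. **Timing.** Complete the list at contacts already in the plan: after the initial bolus, in PACU, and at each daily acute pain service visit until catheter removal.
3. **Relatedness.** Record it as a separate field, and state who judges it and whether that person knows the allocation.
4. **SAP.** State that event rates are compared by arm on all recorded events, with block-related events as a secondary summary.

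The cost is a few more columns in the existing data sheet, a little time at visits that already take place, and more background events counted in both arms. Treatment and sample size do not change.
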